6.15 Subgroup Analysis

Primary and secondary efficacy analyses will be conducted on the overall subject population. Subgroup analyses will be performed to explore the efficacy of esuberaprost in different subject populations. The subgroups will include, but not be limited to:

- age (<65, \geq 65 years);
- sex (males, females);
- race (white, non-white);
- ethnicity (Hispanic or Latino, non-Hispanic or Latino);
- PAH etiology [idiopathic or familial, associated with collagen vascular disease, associated with HIV infection, induced by anorexigens/toxins, associated with repaired congenital systemic-to-pulmonary shunts (repaired \geq 1 years)];
- background PAH therapy (ERA, PDE-5 inhibitor, and riociguat);
- background inhaled treprostinil (experienced or naïve);
- baseline WHO Functional Class;
- years of PAH;
- baseline average 6MWT;
- baseline average Borg Dyspnea Score; and
- country of clinical site (US, Israel).

Continuous covariates will be presented by quartiles. Results will be presented using point estimates and associated 95% CIs both in tables and forest plots. Because the study was not designed to have high power for small or even moderate sized subgroups, these analyses will be considered exploratory.

7 ANALYSIS OF SAFETY

The safety assessments will consist of extent of exposure, AEs including SAEs, laboratory evaluations, vital signs, and ECG findings.

All safety analyses will be based on the Safety Population. No formal inferential testing will be reported for routine safety analyses.

7.1 Extent of Exposure

Exposure to study drug will be calculated as the date of last dose of IMP minus the date of the first dose of IMP plus 1. If the date of last dose of study drug was missing or unknown and the

last drug record had no return date, no assumption will be made for exact exposure. These analyses will include:

- Duration of exposure (in months)
- Number exposed by time (weekly to 3 months, 3-6 months, 6-12 months, 12-24 months, 24-36 months, ≥ 36 months)
- Number exposed by dose (15 μ g, 30 μ g) by time (weekly to 3 months, 3-6 months, 6-12 months, 12-24 months, 24-36 months, ≥ 36 months)
- Maintenance dose during the study (dose subject maintained on IMP after titration period)

Exploratory analyses may be conducted to assess IMP exposure within subgroups (see Sections 6.7.1 and 6.7.2). If appropriate, graphs will display the use of IMP over time.

Similar presentations will be made for inhaled treprostinil use during the study.

7.2 Adverse Events

AEs are recorded throughout the study and at early termination. They are coded using the Medical Dictionary for Regulatory Activities (MedDRA) coding dictionary (the database will document the version current at time of data lock).

7.2.1 Treatment-Emergent Adverse Events

A treatment-emergent adverse event (TEAE) is defined as any event not present prior to the initiation of the IMP or any event already present that worsens in either intensity or frequency following exposure to the IMP.

Only TEAEs occurring after IMP exposure will be summarized. Any AE starting prior to the first dose of IMP (i.e., during the screening period) will be excluded from the summary analyses.

The following notes the planned presentations of TEAEs. Other presentations for TEAEs may be produced to support the sponsor's review and analyses of events of special interest.

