7.12.8 Treatment-Emergent Adverse Events

Treatment-emergent AEs will be defined as events that are newly occurring or worsening from baseline following treatment with study drug.

BPS-314*d* is the active component of BPS-MR. The most frequently reported treatment emergent adverse reactions ($\geq 10\%$) are headache, nausea, diarrhea, flushing, jaw pain, dizziness, pain in extremity, palpitations, pain, fatigue, vomiting, and hot flush.

The most common adverse reactions ($\geq 10\%$) with Tyvaso are cough, headache, nausea, dizziness, flushing (blushing of the skin), throat irritation, pharyngolaryngeal (pharynx and the larynx) pain and diarrhea.

Prostacyclins, as a class, may increase the risk of bleeding and hypotension.

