10.3 Analysis Populations

With the exception of the assessment of vital status until the formal close of the study, the statistical analyses or summaries for efficacy and safety parameters will include evaluations performed from randomization up to the date of the subject's last study visit or 30 days after the permanent discontinuation of study drug. Any additional evaluations will be included in the data listings only.

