10.11 Safety Endpoints

10.11.1 Adverse Events

Adverse events will be recorded throughout the study and at early termination. Adverse events and medical conditions will be coded using the Medical Dictionary for Regulatory Activities (MedDRA) coding dictionary. Treatment-emergent adverse events will be defined as those events, which are newly occurring or worsening from baseline. In all cases only treatment emergent adverse events will be summarized.

Treatment-emergent adverse events will be summarized by treatment group as the number and percentage of subjects having any treatment-emergent AE, having an AE in each body system, and having each individual AE. (*Note: In any given category [e.g., body system] a subject will only be counted once.*) Adverse events will further be categorized by severity, relationship to study drug, and action taken. Other information collected will be listed, as appropriate.

Any event starting more than 5 days after the final dose of study drug will be excluded from the above described tables and only listed, unless the event caused discontinuation from the study

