6.4.2 Handling of Missing Data

The sponsor acknowledges the implications of missing data on the integrity of study outcomes and, consistent with Fleming's recommendations (2011), implemented the following strategies to minimize the extent of missing data:

1. All subjects were allowed to continue in the study until the close of study, whether on IMP or not. Subjects were not to be summarily discontinued from the study, unless 1) the subject withdrew informed consent; 2) the subject met a primary endpoint and declined continuation in the study; or 3) the subject continued to be non-adherent to study protocol after repeated attempts to correct (at least 6 months). However, the subject has the right to discontinue from the study at any time. All subjects who discontinue the study, unless they withdraw informed consent, will continue to be followed, to the extent possible, for vital status until the sponsor concludes the study.
2. Recent publications (Sitbon et al., 2015; Galiè et al., 2015) have shown that roughly 20% of subjects prematurely terminate from mortality and morbidity studies in PAH. The sponsor has throughout the study engaged with study investigators to encourage subjects' retention in the study, adherence with the protocol, and compliance with IMP.
3. While the study protocol is necessarily complex in order to obtain the scientific data to evaluate the safety and efficacy of the IMP, the sponsor designed the protocol in the manner that was not burdensome to the subjects: 1) Much of the data collected for secondary endpoints is derived from assessments performed for 'standard of care' visits; 2) Study visits are minimal (quarterly) with permissive visit windows (\pm 10 days); 3) Use of optional substudies for exploratory endpoints; and 4) Sponsor-provided Tyvaso to all subjects in the study.

Methods for handling missing data will be described in the sections discussing each outcome.

No imputation is planned for missing safety or exploratory data.

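### SAP 7.2.1 sets no end to the treatment-emergent window after the last dose and carries over neither of the protocol's two limits on safety summaries

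*SAP*

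**What the plan says.** **Start of the window.** SAP 7.2.1 gives this definition of a TEAE: "any event not present prior to the initiation of the IMP or any event already present that worsens in either intensity or frequency", once study drug has been taken. The one exclusion is at the front: "Any AE starting prior to the first dose of IMP (i.e., during the screening period) will be excluded from the summary analyses". No SAP section limits onset relative to the last dose.

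**Limits in the protocol.** Protocol 10.11.1 says: "Any event starting more than 5 days after the final dose of study drug will be excluded from the above described tables and only listed", with the exception "unless the event caused discontinuation from the study". Protocol 10.3 restricts efficacy and safety summaries to evaluations from randomization up to the last study visit "or 30 days after the permanent discontinuation of study drug", and sends anything further to listings. It does not say whether the earlier or the later of those two dates governs.

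**Precedence.** SAP Section 1 says that the SAP supersedes the protocol's statistical considerations and that major deviations will be justified in the study report.

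**Follow-up off drug.** SAP 6.4.2 states: "All subjects were allowed to continue in the study until the close of study, whether on IMP or not". SAP 6.12 adds that meeting the primary endpoint did not require a subject to leave. SAP 7.2 has adverse events recorded throughout the study. SAP 7.1 ends exposure at the last dose.

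**The concern.** A subject can stop study drug, stay in the study, and go on having adverse events recorded. Under SAP 7.2.1 each new event is treatment-emergent, however long after the last tablet it starts. The main tables in SAP 7.2.7 are numbers and percentages of subjects by arm with no adjustment for exposure time, so a longer window can only raise them.

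Two things are at stake. First, events that arise off drug in both arms dilute the contrast. Second, Protocol 2.1 expects study drug to continue until parenteral prostanoid therapy is added or the lung is transplanted. Some off-drug time will therefore be time on a parenteral prostacyclin, and its adverse events would be tabulated under the randomized arm. If the arms differ in how many subjects stop, when they stop, or what they then receive, the comparison can be biased. The exposure tables would also cover a shorter period than the TEAE tables beside them.

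**Working it through.** The plan gives no figure on this point to reproduce, so the check compares the texts and then gives an illustration of size.

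**1. The rules side by side**

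| Source | Events tabulated after the last dose |
|---|---|
| Protocol 10.11.1 | Onset up to 5 days; later events listed only, unless they caused study discontinuation |
| Protocol 10.3 | Up to the last study visit or 30 days after permanent discontinuation |
| SAP 7.2.1 | No end stated |

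With no end stated, the window runs to the end of recording. Protocol 7.12.2 puts that at 7 days after the last study visit for adverse events and 30 days for new serious ones.

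**2. One subject**

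Assume the subject stops at month 6 and stays until the study closes at month T. Off-drug days = (T − 6) × 30.44.

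- T = 12: about 183 days
- T = 24: about 548 days
- T = 36 (about the maximum treatment duration in Protocol 4.3): about 913 days

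Now take an event unrelated to drug at a constant yearly rate r. The chance of at least one in a window of w years is 1 − exp(−r × w). The window is 0.5 + 5/365.25 = 0.514 years with the 5-day cut, 0.5 + 30/365.25 = 0.582 years with a 30-day cut, and T/12 years with no cut.

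| r per year (assumed) | 5-day cut | 30-day cut | No cut, T = 12 | T = 24 | T = 36 |
|---|---|---|---|---|---|
| 0.1 | 5% | 6% | 10% | 18% | 26% |
| 0.3 | 14% | 16% | 26% | 45% | 59% |

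**3. The whole trial**

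Inputs from the documents are 240 subjects, accrual over 1.5 years and total duration 2.5 years (SAP 4.1). With uniform accrual, which is an assumption, potential follow-up runs from 1 to 2.5 years, so the mean is (1 + 2.5)/2 = 1.75 years. Total person-time is 240 × 1.75 = 420 years.

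The share who stop drug yet stay to close, and the time at which they stop, are also assumptions. Off-drug share = (240 × share × (1.75 − stop time)) / 420.

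| Share who stop and stay | Stop at month 6 | Stop at month 12 |
|---|---|---|
| 5% (12 subjects) | 12 × 1.25 = 15; 15/420 = 4% | 12 × 0.75 = 9; 9/420 = 2% |
| 10% (24) | 24 × 1.25 = 30; 30/420 = 7% | 24 × 0.75 = 18; 18/420 = 4% |
| 20% (48) | 48 × 1.25 = 60; 60/420 = 14% | 48 × 0.75 = 36; 36/420 = 9% |

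These are shares of person-time. They are not the shift in the planned tables, which count subjects.

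**The case against.** **The protocol's own TEAE definition is open-ended too.** Protocol 7.12.8 speaks of "events that are newly occurring or worsening from baseline following treatment with study drug", again with no end. A reader might infer that the SAP lengthened a bounded definition. It did not: the 5-day rule is a filter on the tables, and it has an exception. This stands. The consequence for the tables is the same, because the filter is what the SAP lacks.

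**The omission may not be a decision.** Protocol Section 10 says that changes of method will be documented in the SAP, and the SAP records none here. SAP 6.2 promises an addendum on data conventions before unblinding, which could set a window. So the documents do not support the inference that the sponsor chose to abolish the limit. Equally, the addendum is not among the documents and SAP 6.2 does not say that it will cover adverse events, so the gap remains.

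**Off-drug time may be short.** Protocol 2.1 and 7.14 press subjects to stay on drug. Withdrawn subjects are weaned and given an End of Study visit. Protocol 7.10.1 has participation end at an adjudicated worsening event. This limits the size, but SAP 6.4.2 and 6.12 let subjects continue, and SAP 6.2 counts as completers those still in the study off drug.

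**Other tables help.** SAP 7 plans no formal testing of routine safety data. SAP 7.2.4 to 7.2.8 also tabulate events by investigator-judged relationship and by action taken. Protocol 10.3.3 allows all available data, as appropriate. These soften the effect but do not separate on-drug from off-drug onset.

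**Conclusion.** The point holds as a gap in the SAP's safety analysis. As written, off-drug events count as treatment-emergent for as long as the subject stays in the study, and neither protocol limit carries over. The primary efficacy analysis is not affected.

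The size is unknown. The documents do not say how many subjects stayed in the study off drug, or for how long. Months of off-drug counting is what the rule permits for an individual, not an observed amount. The 4% to 14% range rests on 5% to 20% stopping at month 6 with all of them staying to close; stopping at month 12 gives 2% to 9%.

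Two stronger readings are tempting and are not supported:

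- **That 14% is the expected share.** The only 20% in the documents (SAP 6.4.2) is the share who left other pulmonary arterial hypertension (PAH) studies early. Subjects who leave the study add little off-drug time, so that figure does not support the upper end.
- **That placebo subjects moving to parenteral prostacyclin would mask the study drug's side effects.** This needs more switching, with continued follow-up, on placebo than on active drug, and the documents do not establish that. Protocol 7.12.8 lists headache, flushing and jaw pain for beraprost; the class risks it names are bleeding and hypotension. The bias can go either way.

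**What to change.** Before unblinding, state one end of window in SAP 7.2.1, as a number of days after the final dose. Reconcile it with Protocol 10.3 and 10.11.1, saying which limit is followed and why. Either keep or explicitly drop the exception for events that caused study discontinuation. Summarize TEAEs within that window, and tabulate later events separately as post-treatment, by randomized arm. Because SAP 7.1 makes no assumption about exposure when the last-dose date is missing, add a rule for placing the end of the window in those subjects.

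The cost is a few sentences and one extra table. The downside is that late effects of the drug would appear only in the post-treatment table, so the two tables should be read together. No safety information is lost.

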7.12 Adverse Events Assessments

7.12.1 Performing Adverse Events Assessments

The clinical site personnel will monitor all AEs throughout the study, from the time of the subject's Informed Consent signature until the end of the subject's study participation (see Appendix 1). At all study site visits and during phone calls to the subject by clinical site personnel, reports of AEs will be elicited by a verbal probe ("How are you feeling?"). Subjects will be encouraged to contact the clinic to report an AE at any time. Appropriate measures, including medical intervention and/or procedures, will be instituted if clinically indicated at the discretion of the Investigator.

All AEs occurring during the study must be documented in the subject's source documents and in the CRFs for AEs. For each AE, the Investigator will evaluate the intensity and seriousness, as well as the relationship to study drug and/or background therapies. Information relating to the AE, such as onset and cessation date and times, escalation, frequency, action taken, and outcome will also be documented (see Appendix 7) in the CRFs for AEs. Where possible, AEs should be
recorded using standard medical terminology. If several signs or symptoms are clearly related to a medically defined diagnosis or syndrome, the diagnosis or syndrome should be recorded on the CRFs for AEs, not the individual signs and symptoms.

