Appendix 7 Adverse Events

The Investigator or designee will probe each subject for any adverse events which may have occurred. When possible, always ask the same question when conducting the verbal probe in order to ensure uniformity between subjects. The subject should be asked:

"How have you been doing (feeling) since your last visit?" "How are you doing (feeling) now?"

Based on the subject's response to these questions, the subject should be asked additional questions relevant to any specific complaint such as:

"Have you had this symptom in the past?"

"How severe is/was the symptom?"

"How often did the symptom occur?"

"How long did the symptom last?"

"Did you take any medication to treat the symptom?"

"Did you see a physician or go to the hospital because of this symptom?"

All adverse events should be fully documented on the CRFs.

DEFINITIONS

An **adverse event (AE)** is defined as any untoward medical experience/occurrence associated with the use of a drug in humans, whether or not it is considered drug related. An AE may include an intercurrent illness, injury, or any other concomitant impairment of the subject's health, as well as abnormal laboratory findings if deemed to have clinical significance. AEs may also include worsening of an existing symptom or condition or post-treatment events that occur as a result of protocol-mandated procedures.

A serious adverse event (SAE) is an AE occurring that has results in any of the following outcomes:

- Results in death
- Is life-threatening (i.e., the subject was, in the opinion of the Investigator, at immediate risk of death from the event as it occurred; it does not include an event that, had it occurred in a more severe form, might have caused death)
- Requires in-patient hospitalization or prolongation of existing hospitalization
- Results in persistent or significant disability/incapacity (i.e., substantial disruption of a person's ability to conduct normal life functions).
- Results in a congenital anomaly/birth defect in an offspring of a study subject
- Other medically significant event that, based upon appropriate medical judgment, may jeopardize the subject and may require medical or surgical intervention to prevent one of the outcomes listed above, e.g., allergic bronchospasm requiring intensive treatment in an emergency room or home, blood dyscrasias or convulsions that do not result in hospitalization, or the development of drug dependency or drug abuse.

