7.2.2 Date of Onset of Adverse Event

The onset date of each AE will be assigned the date recorded on the eCRF.

If the day part of the onset date is missing, then the onset date will be imputed as having occurred on the first day of the given month and year; however, when the first dose of IMP was taken in the same given month and year, then the onset date will be imputed as the day of the first dose of IMP.

If the month and day of the onset date are missing, then the onset date will be imputed as having occurred on the first month and first day of the given year; however, when the first dose of IMP was taken in the same given year, then the onset month and day parts will be imputed as the month and day of the first dose of IMP.

In the unlikely event that the onset date is fully missing, then the onset date will be set to the date of first dose of IMP.

If the imputed date is later than the reported stop date, the imputed date will be set equal to the stop date. This conservative scheme ensures that an AE with partial or complete onset date will be treated as a TEAE.

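### SAP 7.2.1 counts worsening of a pre-existing event as treatment-emergent, then excludes every AE that started before the first dose, with no exception for worsening

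*SAP*

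**What the plan says.** **SAP 7.2.1** defines a TEAE in two parts. One is an event not present before IMP. The other is "any event already present that worsens in either intensity or frequency following exposure to the IMP". The section then limits the summaries to TEAEs occurring after exposure and states: "Any AE starting prior to the first dose of IMP (i.e., during the screening period) will be excluded from the summary analyses".

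**SAP 7.2.2** fixes the date that the exclusion uses: "The onset date of each AE will be assigned the date recorded on the eCRF". The remaining rules there deal with partial or missing dates. None gives a worsened event a new date.

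**Protocol 7.12.1** has AEs collected from informed consent onward, so run-in events are in the AE data. For each AE, information "such as onset and cessation date and times, escalation, frequency, action taken, and outcome will also be documented". **Protocol 7.12.2** has the AE forms updated as new information arrives. **Protocol Appendix 7** says "AEs may also include worsening of an existing symptom or condition".

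The protocol's own definitions also include worsening: "Treatment-emergent AEs will be defined as events that are newly occurring or worsening from baseline following treatment with study drug" (7.12.8) and "Treatment-emergent adverse events will be defined as those events, which are newly occurring or worsening from baseline" (10.11.1). Section 10.11.1 has no exclusion for a pre-dose start. Its only date cut concerns events starting more than 5 days after the final dose.

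**The concern.** An event already present before IMP must have started before IMP. Read literally, the exclusion removes the very events that the second part of the definition brings in, unless the worsening has its own record with a later onset.

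The case is foreseeable in this trial. Subjects not on inhaled treprostinil start it during screening (Protocol Appendix 2) and take it for 90 days before randomization. Protocol 7.12.8 lists headache, nausea, diarrhea, flushing and dizziness as common with both BPS and inhaled treprostinil. A run-in symptom of this kind that worsens when a second prostanoid is added is something an add-on safety table should show.

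The filter acts before every table in SAP 7.2.7 and 7.2.8. A dropped record leaves the preferred-term and severity rows and, where relevant, the serious-TEAE row and the row for TEAEs leading to IMP discontinuation. For these records, what the tables show would depend on how a site entered the worsening and not on the SAP's definition.

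**Working it through.** The check is mainly logical. Each kind of record is put through both rules of SAP 7.2.1, with onset taken from the eCRF as SAP 7.2.2 directs.

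| Record | TEAE by definition? | Removed by start-date rule? | Result |
|---|---|---|---|
| Starts after first dose | Yes | No | Consistent |
| Starts and ends before first dose | No | Yes | Consistent |
| Starts before first dose, ongoing, does not worsen | No | Yes | Consistent |
| Starts before first dose, ongoing, worsens; worsening entered as a new AE with post-dose onset | Yes (new record) | No | Consistent |
| Starts before first dose, ongoing, worsens; same record updated | Yes | Yes | **Conflict** |

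Only the last row conflicts, so the next question is whether the documents rule it out.

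- **Record keeping.** Protocol 7.12.1 treats escalation and frequency as information about an AE, and 7.12.2 has AE forms updated. A single record that keeps its pre-dose onset is therefore a realistic practice. Appendix 7 permits worsening to be an AE but does not require a new record or a new date.
- **Medical history.** If the earlier symptom sits only in medical history and its worsening is entered as an AE, nothing is lost. But Protocol 10.11.5 sends pre-randomization findings to medical history only for physical examination. Protocol 7.3, 7.4, 7.7 and 7.8.1 send clinically significant changes after consent to the AE form.
- **Date rules.** SAP 7.2.2 does not re-date worsening.

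So the documents allow the last row.

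**When an affected AE can begin.** Screening is 3 to 120 days before Baseline (Protocol 8.1), and the first dose is on Baseline Day 2 (SAP 6.3.1). From Screening to first dose is 3 + 1 = 4 to 120 + 1 = 121 days. For subjects who start inhaled treprostinil in the run-in it is at least about 90 + 1 = 91 days. This shows opportunity, not frequency: the AE must also be ongoing at first dose and then worsen.

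**Weight of one subject.** SAP 4.1 plans about 120 subjects per arm. If about 120 are dosed, one dropped subject lowers that arm's percentage for the term by 1/120 = 0.83 percentage points. The effect is 0 if the subject has another post-dose record of the same preferred term, because SAP 7.2.8 counts a subject once per term. The documents give no rate of worsening, so no total can be computed.

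**The case against.** The strongest reply is that no event need be lost. Protocol 11.7 requires CRF entries to follow completion guidelines. These are not available here and may tell sites to close a worsened AE and enter it again with a new onset date. SAP 6.2 also promises a data-conventions addendum before unblinding. This stands as far as it goes: it makes the actual loss uncertain, but it does not change the rule as written.

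A second reply is that the exclusion only restates that screening AEs which are not TEAEs are left out. The authors may have meant that. But the sentence excludes by start date, and a programmer following it would filter on start date.

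A third reply is that the pool is narrow. Randomization requires 90 uninterrupted days on inhaled treprostinil and at least 30 days at a stable dose (Protocol 5.2), after a run-in meant to ensure tolerability. That is fair and supports a small effect.

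Three stronger readings are tempting, and the documents do not support them:

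- **A clash with SAP 7.2.2.** That section calls its date rules conservative ("This conservative scheme ensures that an AE with partial or complete onset date will be treated as a TEAE"), so a reader might say that it counts missing dates but rejects known ones. Those rules resolve unknown timing, and a known pre-dose date needs no imputation. Nor is a missing onset always counted: where the stop date is before the first dose, the onset is set to the stop date.
- **A departure from Protocol 7.12.8.** That section only defines a TEAE, and the SAP's definition matches it. Protocol 10.11.1 is a statistical consideration, which the SAP says it supersedes. The conflict is internal to SAP 7.2.1.
- **0.83 points as a ceiling per subject.** Enrolment is approximate, and the Safety Analysis Population contains dosed subjects by treatment received (SAP 6.1). With fewer than 120 in an arm, one subject weighs more.

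**Conclusion.** SAP 7.2.1 contradicts itself for one kind of record: an AE that starts before the first dose, is ongoing at that dose and worsens on IMP under the same record. That much follows from the text alone. A reader might infer that such events will be missing from this trial's tables. The documents do not support that, because they do not show how sites entered worsening.

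The point is minor. The number of subjects affected cannot be derived and is probably small. Each is worth about 0.8 points for a term, assuming about 120 dosed subjects in the arm and no other post-dose record of that term. SAP 7 plans no formal testing of routine safety data, the rule applies to both arms, and reasons for discontinuation are tabulated separately under SAP 6.5. The same rule in both arms does not guarantee an equal effect: if IMP does worsen run-in symptoms, more records would be dropped on esuberaprost than on placebo.

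**What to change.** Replace the exclusion sentence in SAP 7.2.1 with:

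*AEs that started before the first dose of IMP are excluded unless they worsened in intensity or frequency after the first dose; those that worsened are counted as TEAEs.*

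In the data-conventions addendum promised in SAP 6.2, state:

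- how post-dose worsening is identified and dated from the escalation information that Protocol 7.12.1 requires;
- that the recorded AE intensity is used where no separate post-dose grade exists. Appendix 7 describes one three-point grade per AE, and the documents do not show that escalation is graded or dated, so a rule needing the worst post-dose grade might not be workable.

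The cost is one sentence, one entry in an addendum already planned, slightly more programming, and possibly a few data queries while the study is still blinded.
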